#### ***5.3.4 Dose Optimization Period (Week 1, Week 2, Week 3, Week 4 and Week 5)***

Day 1-6, Day 8-13, Day 15-20, Day 22-27 and Day 29-34 – Home Days (actual days may vary due to permissible window around Day 7, Day 14, Day 21, Day 28, and Day 35). Procedures to be performed:

1. Parent/caregiver/subject will visually inspect the application site for irritation before application and complete the daily dermal evaluation diary as instructed.
2. Parent/caregiver/subject will apply the patch in the morning daily and remove the patch daily as instructed.

Amendment 4: Version 5.0 May-08-2013

Amendment 3: Version 4.0 December-11-2012

Amendment 2: Version 3.0 October-31-2012

Amendment 1: Version 2.0 August-02-2012

Final Protocol May-25-2012

3. Parents/caregivers/subjects will complete the daily dosing diary and daily dermal evaluation diary.
4. Parents/caregivers will complete the CPRS-R:S on the day prior to clinical visit: Day 6, Day 13, Day 20, Day 27 and Day 34.
5. Parent/caregiver/subject will call the site to report any AEs or concomitant therapy.

#### 5.3.4.1 Day 4, Day 11, Day 18, Day 25 and Day 32– Telephone Contact

Site personnel will contact subject or parent or caregiver by telephone on Day 4, Day 11, Day 18 Day 25 and Day 32 (Due to the 3 day window around clinic days, the day of the actual telephone call may vary. The call should occur approximately mid-way between clinic visits). During the telephone call the following procedures are to be performed:

1. Review concomitant therapy and adverse events, if any. Record new information.
2. Remind the subject and parent/caregiver that per protocol subjects should not receive medications or therapy to treat ADHD other than the study medication.
3. Remind parents/caregiver/subject to be compliant with patch application and removal and to comply with the study drug dosing regimen.
4. Subjects/parents/caregivers will be reminded to continue completing the daily dosing diary and daily dermal evaluation diary.
5. Subjects/parents/caregivers will be reminded to complete the CPRS-R:S.
6. Subjects will be informed as to the time and date of next study visit and the importance of having the subject keep that visit.
7. Subjects/parents/caregiver will be instructed to save all unused and used patches and bring them to their clinic visits.
8. Subjects/parents/caregiver will be instructed to call the site personnel to report any AEs and concomitant therapy.

#### 5.3.4.2 Visit 1 (Day 7), Visit 2 (Day 14), Visit 3 (Day 21), Visit 4 (Day 28) and Visit 5 (Day 35) – Clinic Days

Subjects will return to the clinic for evaluations on Day 7  $\pm$ 3 days, Day 14  $\pm$ 3 days and Day 21  $\pm$ 3 days, Day 28  $\pm$ 3 days and Day 35  $\pm$ 2 days. There must be at least 4 days in between clinic visits). The following evaluations will be performed during each clinic visit:

1. Record any AEs or concomitant therapy since previous visit.

Amendment 4: Version 5.0 May-08-2013

Amendment 3: Version 4.0 December-11-2012

Amendment 2: Version 3.0 October-31-2012

Amendment 1: Version 2.0 August-02-2012

Final Protocol May-25-2012

2. Perform drug accountability and collect all used and unused patches.
3. Review the daily dosing and irritation diaries for compliance.
4. Obtain vital signs (sitting BP, HR, RR, oral body temperature).
5. Record weight.
6. Perform a 12-lead electrocardiogram (ECG) on Day 35.
7. Perform urine pregnancy testing on all female subjects of child-bearing potential.
8. Obtain ADHD-RS-IV score (home version).
9. Perform 1 PERMP (for practice on days 7, 14, 21, and 28) at demonstrated level.
10. Half-day classroom with SKAMP and PERMP (Visit 5, Day 35) pre-dose and 1 and 2 hours post-dose (SKAMP and PERMP rating periods will be 20 minutes in duration).
11. Patch application in clinic (Day 35 only) by subject/parent/caregiver/site personnel
12. Adhesion and discomfort will be evaluated by site personnel after d-ATS patch application at 1 hour and 2 hours/ immediately prior to leaving the clinic on Visit 5 (Day 35).
13. For discomfort scores greater than 0, discomfort will also be evaluated at 1 and 2 hours after d-ATS patch application on Visit 5 (Day 35) using the 10-point Wong-Baker Faces or Visual Analog Scale (age dependent). A  $\pm$  15 minute window is permissible.
14. Site personnel will evaluate skin irritation of the previous day's patch near subject dismissal on Visit 5 (approximately 19 hours after removal of the patch).
15. Administration of the C-SSRS (Children's Since Last Visit version) by a trained staff member.
16. Perform CGI-I.
17. Based on the ADHD-RS-IV score, CGI-I score and side effect profile, adjust the subject's dose to the next available dose (except Visit 4, which can only be a dose reduction and Visit 5 (randomization at optimal dose))
18. If the subject is unable to reach optimal dose, discontinue the subject in IVRS/IWRS and proceed to or schedule the early termination visit.
19. Contact IVRS/IWRS to obtain study medication pack number and dispense study medication on Day 7, Day 14, and Day 21, and 28.

Amendment 4: Version 5.0 May-08-2013

Amendment 3: Version 4.0 December-11-2012

Amendment 2: Version 3.0 October-31-2012

Amendment 1: Version 2.0 August-02-2012

Final Protocol May-25-2012

20. On Day 28, after receiving the pack number from IVRS/IWRS, prior to dispensing, remove one pouch from the medication pack, fill in applicable subject information on the label, and retain the pouch for application in the clinic on Day 35.
21. On Day 35, contact IVRS/IWRS to randomize the subject in the system. After receiving the pack number, prior to dispensing, remove one pouch from the medication pack, fill in applicable subject information on the label, and retain the pouch for application in the clinic on Day 42.
22. Dismiss from clinic.

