## **5 INVESTIGATION PLAN**

### **5.1 Study Design**

This is a randomized, double-blind, cross-over, placebo controlled study to evaluate the safety and efficacy of d-ATS (5 mg/ 4.76 cm^2, 10 mg/ 9.52 cm^2, 15 mg/14.29 cm^2 and 20 mg/19.05 cm^2) in children and adolescents 6 to 17 years of age with ADHD.

The study will consist of a four-week screening period, a one-week wash-out period (if applicable), a five-week open-label, step-wise dose optimization period and two-week double blind randomized crossover treatment period with weekly classroom assessments and a safety follow-up by telephone 7 - 10 days after last dose of study drug.

**Screening Period (Visit -1):** Screening procedures may be performed within four weeks prior to the Dose Optimization Period of the study.

**Washout Period:** Eligible subjects will undergo a 72 hour wash-out period if applicable.

**Baseline Visit (Day 0, Visit 0):** Eligible subjects will return to the clinic on Day 0 for baseline assessments. Subjects who continue to meet the eligibility criteria will be entered into the open-label Dose Optimization period.

**Dose-Optimization Period [Day 1 to Day 35; Visit 1 (Day 7 ±3 days), Visit 2 (Day 14 ±3 days), Visit 3 (Day 21 ±3 days), Visit 4 (Day 28 ±3 days) and Visit 5 (Day 35 ±2 days)]:**

Following Screening Period and Washout Period (if applicable), eligible subjects will enter the open-label Dose-Optimization Period, during which they will begin receiving d-ATS followed by evaluation for efficacy and tolerability of that dosage approximately 7 days later. Dosage will

Amendment 4: Version 5.0 May-08-2013

Amendment 3: Version 4.0 December-11-2012

Amendment 2: Version 3.0 October-31-2012

Amendment 1: Version 2.0 August-02-2012

Final Protocol May-25-2012

be initiated at 5 mg/ 4.76 cm^2 d-ATS and adjusted to the next available dose at weekly intervals, until optimal dose is reached. Optimal dose will be defined as the dose that will produce a reduction in ADHD RS-IV score  $\geq 30\%$  and CGI-Improvement (CGI-I) score of 1 or 2 and has tolerable side effects.

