Tolerability will be determined by the investigator, based on review of AEs and clinical judgment. Once reached, the optimal dose will be maintained for the remainder of the Dose-Optimization Period. Investigator can increase the current dose to provide additional symptom control. One dose reduction will be permitted if the subject experiences unacceptable tolerability of the current dose.

Subjects will be discontinued if they are unable to tolerate d-ATS or cannot reach their optimal dose by Week 5. If the subject has reached their optimal dose, then at the discretion of a medically qualified investigator, one dose reduction per participant may occur during the dose optimization period for safety reasons. However if the current dose is intolerable and the subject has never reached their optimal dose, the subject would be discontinued from the study. A dose increase may occur at visit 4 if no prior dose has met criteria for optimal response and the current dose is well tolerated as deemed by a medically qualified investigator. The dose used during the week 5 visit will be the dose that the subject is randomized to during the Double-Blind Treatment Period.

During Visit 5 (Day 35  $\pm$  2 days), subjects will attend a half-day practice laboratory school with analog classroom sessions to become familiar with classroom schedules and procedures. Three SKAMP assessments will be performed, and 3 practice PERMP tests will be given during the practice session.

Subjects will return to the clinic for evaluations and dose adjustments on Visit 1 (Day 7  $\pm$  3days), Visit 2 (Day 14  $\pm$  3days), Visit 3 (Day 21 $\pm$  3days), Visit 4 (Day 28  $\pm$  3days) and for evaluations (no further dose adjustments) and randomization on Visit 5 (Day 35)  $\pm$  2days (see schematic below). Site personnel will contact subjects by telephone on Day 4, Day 11, Day 18, Day 25 and Day 32 or midway between visits. Subjects/parents/caregivers will be instructed to complete a daily dosing diary and a daily dermal diary. All end of study procedures will be completed for subjects who are early discontinuations from the study.

Visit/Week	d-ATS	Evaluations
Visit 0/Week 1	5 mg d-AMP/ 4.76 cm  patch (4-10doses)	ADHD RS-IV, CGI-Improvement (CGI-I) and AEs and PERMP

Amendment 4: Version 5.0 May-08-2013

Amendment 3: Version 4.0 December-11-2012

Amendment 2: Version 3.0 October-31-2012

Amendment 1: Version 2.0 August-02-2012

Final Protocol May-25-2012

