**Double-Blind Treatment Period [Day 36 to Day 49; Visit 6 (Day 42) and Visit 7 (Day 49)]:**

Subjects who have reached an optimal dose will be randomized at Visit 5 to receive double-blind treatment. Administration of study medication will begin on Day 36 and continue up to Day 49 (end of Week 7). During Week 6 subjects will receive study patches in accordance with the randomization schedule and during Week 7 subjects will cross-over to receive the other study treatment per the randomization schedule. Subjects/parents/caregivers will be instructed to apply study patches to the hip once daily in the morning at approximately 8:00 am. Patches will be removed after 9 hours. Each day a new patch will be applied to the opposite hip. Subjects will be instructed to continue completing the daily dosing diary and the daily dermal diary. Subjects will return to the clinic for evaluations and analog classroom sessions in the laboratory classroom setting on Visit 6 (Day 42) and Visit 7 (Day 49). Site personnel will contact subjects by telephone on Day 39 and Day 46. All end of study procedures will be completed for subjects who are early discontinuations from the study.

**Follow-Up:** A safety follow-up by telephone 7- 10 days (Visit 8, Day 56 + 3 days) after last dose of study drug.

**Sample Size:** Sufficient number of subjects with ADHD will be screened to randomize approximately 90 subjects. Assuming a 20% dropout rate, it is expected that 74 subjects will complete the study. The Full Analysis Set population (FAS) will be used as the primary population for analysis of efficacy endpoints and is defined as subjects who have taken at least one dose of study medication.

Amendment 4: Version 5.0 May-08-2013

Amendment 3: Version 4.0 December-11-2012

Amendment 2: Version 3.0 October-31-2012

Amendment 1: Version 2.0 August-02-2012

Final Protocol May-25-2012

**Study Duration:** The duration of the study will be approximately 56 days for each individual subject (not including screening and washout).

**Study Population:** The study population will consist of children and adolescents 6 to 17 of age, who have been diagnosed with ADHD.

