1.1 CHANGES FROM PROTOCOL

There are no changes from protocol amendment 4, dated 08 May 2013.

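### The protocol gives two incompatible rules for changing the dose at Visit 4, which matters for children still below 20 mg who tolerate their dose and have met no optimal dose

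*Protocol*

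**What the plan says.** Four places state what may happen to the dose at Visit 4 (Day 28).

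- Protocol 5.3.4.2, step 17, is the visit procedure. Staff move the child to the next dose on the basis of ADHD-RS-IV, CGI-I and side effects, "except Visit 4, which can only be a dose reduction".
- Protocol 5.1 says: "A dose increase may occur at visit 4 if no prior dose has met criteria for optimal response". It adds the condition that a medically qualified investigator judges the current dose well tolerated.
- The protocol synopsis and SAP section 3 repeat that sentence and its condition.

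The surrounding rules give Visit 4 its weight. Titration is weekly, "adjusted to the next available dose at weekly intervals, until optimal dose is reached". Visit 5 is "for evaluations (no further dose adjustments) and randomization on Visit 5", so Visit 4 is the last visit at which the dose can change. Section 5.1 adds: "Subjects will be discontinued if they are unable to tolerate d-ATS or cannot reach their optimal dose by Week 5". Step 18 of 5.3.4.2 carries this out: "If the subject is unable to reach optimal dose, discontinue the subject in IVRS/IWRS". On entry to the blinded phase: "Subjects who have reached an optimal dose will be randomized at Visit 5 to receive double-blind treatment". The dose in use at the Week 5 visit is the one carried into that phase.

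The SAP does not settle the matter. Section 1.1 states: "There are no changes from protocol amendment 4, dated 08 May 2013".

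**The concern.** Step 17 is the instruction a site has in hand during the visit, and its wording excludes any increase. The design text allows one under stated conditions. A site that follows one passage departs from the other.

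The Visit 4 decision comes just before two irreversible steps: the test of whether an optimal dose was reached, and the fixing of the double-blind dose. The rule applied can therefore affect who enters the crossover and at what strength. It can also affect the optimised-dose subgroup that protocol 8.2.1 and SAP 7.1.1 prespecify. Apart from the analysis, a dosing instruction in a paediatric trial of a Schedule II stimulant should not have two versions.

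**Working it through.** No sample size, power or event figure bears on this point, so there is no stated figure to reproduce. The check has two parts: comparing the texts, and listing which children the two rules treat differently.

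**Texts side by side**

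| Place | Increase at Visit 4 | Condition |
|---|---|---|
| Protocol 5.3.4.2, step 17 | No, reduction only | None stated |
| Protocol synopsis | Yes | No optimal dose so far, current dose well tolerated |
| Protocol 5.1 | Yes | Same |
| SAP section 3 | Yes | Same |

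The last three share one sentence, so they are one rule stated three times rather than three independent confirmations. The Visit 4 row of the dose table in 5.1 shows only the optimal dose and mentions neither an increase nor a reduction, so it does not decide between the rules. No passage gives an order of precedence.

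**Who is affected**

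Inputs: the available strengths are 5, 10, 15 and 20 mg (protocol Table 6). The dose table in 5.1 assigns 5 mg at Visit 0, 10 mg at Visit 1, and then 15 mg at Visit 2 and 20 mg at Visit 3 unless an optimal dose has already been found.

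Take a child who tolerates every dose and never meets the optimal criteria. Let h be the number of weekly steps held at Visits 1 to 3.

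- Dose worn into Visit 4 = 20 − 5h mg.
- Highest dose after Visit 4 if an increase is allowed = the smaller of (20 − 5h) + 5 and 20 mg.
- Highest dose after Visit 4 if only a reduction is allowed = 20 − 5h mg.

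| h | Dose into Visit 4 | Maximum, increase allowed | Maximum, reduction only |
|---|---|---|---|
| 0 | 20 mg | 20 mg | 20 mg |
| 1 | 15 mg | 20 mg | 15 mg |
| 2 | 10 mg | 15 mg | 10 mg |
| 3 | 5 mg | 10 mg | 5 mg |

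With h = 0 the rules give the same ceiling. With h = 1, 2 or 3 they differ by one strength.

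**What follows for an affected child**

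If an increase is allowed, the child can try one higher strength and be judged on it at Visit 5. If only a reduction is allowed, the child can still stay on the present dose, because step 17 limits the direction of a change and does not require one. That child may meet the criteria at Visit 5 and be randomised at the lower strength, or may fail them and be discontinued. The rules can therefore lead to different double-blind doses, or to randomisation under one and discontinuation under the other.

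**The case against.** The strongest reply is that the conflict reaches few children and leaves the main comparison alone. Most of this stands.

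- **Reach.** A reader might infer that every child not optimised by Visit 4 is affected. The dose table does not support that: a child moved up on schedule is already on the top strength. The rules diverge only if an earlier weekly step was held. Still, the increase sentence would have no use unless the authors expected some such children.
- **Outcome.** A reader might infer that each affected child is either escalated or withdrawn. Section 5.1 sets the test at Week 5, not at Visit 4, and a child kept on the same dose can still pass it.
- **Site differences.** A reader might infer that a child would be randomised at one site and withdrawn at another. Day 28 packs are issued through IVRS/IWRS (5.3.4.2, step 19). If that system enforces one rule, site differences would shrink. The documents do not describe its logic, so divergence can be neither shown nor ruled out. If it does enforce one rule, staff following the other passage would find themselves blocked.
- **Bias.** A reader might infer that the primary result is biased. The conflict acts wholly before randomisation. Each child is then compared on the fixed dose and on placebo, with all d-ATS strengths pooled (SAP 7.1.1).
- **Safety.** The permissive text requires good tolerability, and neither rule goes beyond the studied strengths.

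None of this removes the contradiction. Step 17 still forbids what three other places allow, at the last visit where the dose can change.

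**Conclusion.** The contradiction is real and in current text, and should be corrected. It applies to children below 20 mg at Visit 4 who tolerate their dose and have met no optimal dose. Their number is not given and cannot be derived from the documents.

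For these children the rule followed can shift the double-blind dose by one strength and can change whether they are randomised at all. Across the trial, that could alter the randomised population, the dose mix and the optimised-dose subgroup. SAP 7.1.1 merges subgroups of fewer than 5 subjects, so even a small shift might change which dose levels are reported separately. The calculation of 74 completers from 90 randomised does not depend on this rule, and the within-child primary comparison is not biased.

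The conclusion assumes that titration otherwise follows the dose table in 5.1 and that no site instruction outside these documents already settles the rule. It takes no view on which rule is clinically right.

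**What to change.** Reconcile protocol 5.3.4.2 step 17, the synopsis, protocol 5.1 and SAP section 3 so that one Visit 4 rule appears in all four. The sponsor's clinical team decides which rule that is. The reconciled text should also say plainly whether a never-optimised child may stay on the current dose until Visit 5, since step 17 leaves this to inference. Then confirm that the IVRS/IWRS dispensing logic for Day 28 enforces the same rule.

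The cost is a short protocol amendment (with IRB approval under protocol 9.3.1, since it concerns dosing), a matching edit to the SAP if its sentence changes, a memo to sites, and an IVRS/IWRS check. The statistical analysis does not change.

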### 5.3.5 Double Blind Treatment Period (Week 6 and Week 7)

Following dose optimization, subjects will enter the two-week double-blind treatment period. Subjects will be randomized to receive daily d-ATS or placebo at the optimized dose. During the two-week double blind cross-over treatment period each subject will receive treatment per the randomization schedule as follows:

Optimal d-ATS dose during Dose Optimization Period (Day 1 to Day 35)	Cross-Over, Double-Blind Treatment Period	
	Week 6	Week 7
d-ATS (5 mg/ 4.76 cm  )	d-ATS (5 mg/ 4.76 cm  ) or Placebo	d-ATS (5 mg/ 4.76 cm  ) or Placebo
d-ATS (10 mg/ 9.52 cm  )	d-ATS (10 mg/ 9.52 cm  ) or Placebo	d-ATS (10 mg/ 9.52 cm  ) or Placebo
d-ATS (15 mg/ 14.29cm  )	d-ATS (15 mg/ 14.29cm  ) or Placebo	d-ATS (15 mg/ 14.29 cm  ) or Placebo
d-ATS (20 mg/ 19.05 cm  )	d-ATS (20 mg/ 19.05 cm  ) or Placebo	d-ATS (20 mg/ 19.05 cm  ) or Placebo

During the Double-Blind Period, for the first week subjects will take study drug as per randomization schedule and for the next week they will be crossed over to the other study drug per randomization schedule. During the Double-Blind Period study drug will be administered by the subject/parent/caregiver, however on the last day of each week (analog classroom days Day 42 and Day 49) the study drug will be administered in the clinic by subject/parent/caregiver/site personnel at the start of the laboratory classroom assessment.

Patches will be worn for 9 hours every day. After 9 hours the patch will be removed. Every day a new patch will be applied.

Amendment 4: Version 5.0 May-08-2013  
 Amendment 3: Version 4.0 December-11-2012  
 Amendment 2: Version 3.0 October-31-2012  
 Amendment 1: Version 2.0 August-02-2012  
 Final Protocol May-25-2012

**5.3.5.1 Day 36-41 and Day 43-48 – Home Days**

Procedures to be performed:

1. Parent/caregiver/subject will visually inspect the application site for irritation before application and complete the daily irritation diary as instructed.
2. Parent/caregiver/subject will apply the patch in the morning daily and remove the patch daily as instructed.
3. Parent/caregiver/subject will examine and grade for adhesive residue immediately following patch removal according to the scale presented in section 6.15.4, Table 5.
4. Parents/caregivers/subjects will complete the daily dosing diary and daily dermal evaluation diary.
5. Parents/caregivers will complete the CPRS-R:S on Day 41 and Day 48
6. Parent/caregiver/subject will call the site to report any concomitant medications or AEs.

**5.3.5.2 Day 39 and Day 46 – Telephone Contact**

The site personnel will contact subject or parent or caregiver by telephone on Day 39 and Day 46. During the telephone call the following procedures are to be performed:

1. Review concomitant therapy and adverse events, if any. Record new information.
2. Remind the subject and parent/caregiver that per protocol subjects should not receive medications or therapy to treat ADHD other than the study medication.
3. Remind parents/caregiver/subject to be compliant with patch application and removal and to comply with the study drug dosing regimen.
4. Subjects/parents/caregivers will be reminded to continue completing the daily dosing diary and daily dermal evaluation diary.
5. Subjects/parents/caregivers will be reminded to complete the CPRS-R:S.
6. Subjects will be informed as to the time and date of next study visit and the importance of having the subject keep that visit.
7. Subjects/parents/caregiver will be instructed to save all unused study medication and used study medication and bring them to their clinic visits.
8. Subjects will be instructed to call the site personnel to report any AEs and concomitant therapy.

